All participants will also be administered a set of cognitive assessments immediately prior to program entry. These cognitive tasks will include measures of executive function abilities, visuospatial skills, recognition memory, and tasks of sustained and divided attention. The WCST and the picture and word versions of the Pyramids and Palm Trees Test (PPT) will be administered to assess executive function skills. The PPT was found to correlate with the cognitive factors identified in Lambon Ralph et al.'s study and performance has been shown to depend partially on reasoning and problem-solving abilities^[103]. Additionally, two of the studies found significant correlations between PPT performance and treatment response following naming therapy^[10].

^{66]}. The immediate and delayed recall of the Complex Rey Figure will be administered to evaluate visuospatial abilities and memory. This test has been found to be significantly correlated with naming treatment outcomes^[10]. Two of the short recognition subtests of the Camden Memory Test, the topographical and word subtests, will be administered to assess recognition memory^[66]. Additionally, study participants will be given the sustained and divided attention subtests of the TEA. As noted above, Lambon Ralph and colleagues^[10] found that the elevator counting with distraction subtest on the TEA was one of the significant cognitive factors that predicted naming treatment outcome. The TEA provides an aphasia-friendly, ecologically valid assessment of multiple forms of attention that has been standardized on a group of stroke patients^[104].

Finally, participants will receive structural magnetic resonance imaging scans immediately prior to program entry. Not all participants will be eligible to take part in imaging procedures (due to presence of exclusionary conditions such as claustrophobia or metal in the body). As noted above, current estimates are that approximately 20% of PIRATE participants to date have such exclusionary conditions.

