The first analysis will evaluate whether the social contact associated with PIRATE participation results in improved performance on study measures, independent of any actual aphasia treatment. We will use a multivariate mixed model to test whether there are any differences between the immediate-treatment and delayed-treatment groups at the initiation of treatment, and whether there is any group-by-time interaction suggesting a positive effect of the delayed treatment week. The dependent variables will include performance on treated and untreated naming probes and PNT short forms.

If this analysis finds no significant differences between the groups, it will suggest that any observed treatment gains can be attributed to the SFA treatment rather than general effects of the social contact associated with PIRATE. In this case, the two groups will be collapsed for further analysis. In the unexpected event that this analysis finds a significant difference favoring the delayed treatment condition, it will suggest that observed treatment gains should be attributed to the combination of SFA and the socialization inherent in a residential treatment program, rather than to SFA alone. In this case, we will use the data to estimate the size of the socialization effect and statistically control for it in subsequent analyses, where possible.

C.3.1 Psycholinguistic, cognitive, and neuroanatomical predictors of treatment response

The primary dependent variable for analyses relevant to Specific Aim 1 will be the proportion of correctly-named treated stimuli at study exit (post-treatment), minus the proportion of correctly-named treated stimuli at study entry (pre-treatment). This difference score provides the simplest measure of naming treatment response. Supplementary analyses may be carried out using a related dependent variable, the percentage of possible naming improvement^[10]. This is a derived measure which divides the simple pre-post difference score

by the difference between pre-treatment naming performance and ceiling performance (100% accuracy minus observed pre-treatment accuracy). This measure helps correct for observed differences in baseline accuracy.

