Secondary dependent variables for these analyses will include accuracy on untreated related stimuli (accuracy at study exit minus accuracy at study entry) and Rasch-scaled scores for PNT stimuli (scores at exit minus scores at entry). Previous studies have not found any predictive relationships between neuroanatomical or other variables and generalization to untrained stimuli^[9, 20]. However, those studies did not administer treatment in the amounts or intensities provided in PIRATE or in the proposed research. It is possible that more intensive and/or larger doses of aphasia treatment may uncover stronger generalization effects (as well as stronger predictive relationships) than have previously been reported.

C.3.1.1 Group effects on treatment response

Participants will be classified as having primarily phonological, primarily lexical-semantic, or mixed naming impairments, using the methods described in section C.2.3 above. A between-participants analysis of variance will be carried out on the primary and secondary dependent measures of treatment response, with language-impairment group as an independent variable. As predicted by Hypothesis 1a and consistent with previous findings in the naming-treatment literature^[12, 44], we anticipate that there will not be a main effect of language-impairment group on treatment response. The different groups of naming-impaired individuals will show comparable benefit from intensive, semantically-oriented naming treatment. If group differences are found in the ANOVA, we will explore their source using Tukey's multiple comparisons to control type-I error.

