Participants' performance on the set of cognitive measures identified above (section C.2.3) will be transformed into z-scores, to ensure that the scores may be compared across tasks. These transformed scores will be submitted to principal component analysis in order to identify one or more factors which account for performance across the measures. Based on previous findings^[10, 69], we anticipate that measures of executive function (WCST) and performance on the PPT will load on one factor, while measures of visuo-spatial memory (Rey Complex Figure) and other memory function (Camden Memory Test, topographical and word subtests) will load on a separate factor. Performance on tests of focused and divided attention (TEA) may also load on a separate factor.

These factors will be entered as predictors into separate linear regressions targeting primary and secondary dependent measures, to determine which cognitive factors predict these measures of treatment response. Based on previous results, we anticipate that the executive-function factor^[10, 71], the memory factor^[10, 66], and the attention measures^[10] will all be significant predictors of naming treatment response. If no reliable predictive relationships are found between these cognitive factors and treatment response, we will perform additional correlation analyses to examine the relationship between performance on individual cognitive tasks and treatment response. We may also subtract variance associated with aphasia severity (as assessed by the CAT mean language modality T-score) using stepwise linear regression, since different aphasia severities may be associated with different responses to treatment^[1]. Given that the studies referenced above have demonstrated the hypothesized relationships with sample sizes ranging from 7 to 33 participants, we expect that the present analyses will be sufficiently powered, given the proposed sample size of 50.

C.3.1.3 Voxel-based lesion symptom mapping (VLSM)

For each participant, lesion size and extent will be quantified and related to treatment response using voxel-based lesion symptom mapping (VLSM), to test the neuroanatomical hypotheses relevant to Specific Aim 1. These analyses will compare the structural MRI data collected for study participants with change scores based on their performance on outcome measures.

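### After a null factor analysis, about nine single-task correlations run with no multiplicity control: roughly a 17–35% chance of a false predictor on one outcome, 40–71% on three

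*Combined protocol and SAP*

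**What the plan says.** Section C.3.1.2 standardises the cognitive scores, reduces them by principal component analysis, and enters the resulting factors in regressions on the primary and secondary outcomes. The number of factors is not fixed in advance. The fallback has a results-dependent trigger: "If no reliable predictive relationships are found between these cognitive factors and treatment response", then "we will perform additional correlation analyses to examine the relationship between performance on individual cognitive tasks and treatment response". No significance level, number of tests, list of outcomes or adjustment is given for that step.

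The tasks are listed in section C.2.3:
- "The WCST and the picture and word versions of the Pyramids and Palm Trees Test (PPT) will be administered to assess executive function skills": three scores.
- "The immediate and delayed recall of the Complex Rey Figure will be administered": two scores.
- "Two of the short recognition subtests of the Camden Memory Test, the topographical and word subtests": two scores.
- "study participants will be given the sustained and divided attention subtests of the TEA": at least two scores.

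The outcomes are in section C.3.1: "The primary dependent variable for analyses relevant to Specific Aim 1 will be the proportion of correctly-named treated stimuli at study exit", taken as a change from entry. Then: "Secondary dependent variables for these analyses will include accuracy on untreated related stimuli", followed by the change in the Rasch-scaled Philadelphia Naming Test score. That is one primary and two secondary outcomes.

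Elsewhere the plan does control error: Tukey comparisons for impairment groups (C.3.1.1), a false discovery rate of .05 for lesion mapping (C.3.1.3), and Bonferroni-corrected t-tests with a familywise rate of 0.1 for the pairwise comparisons (C.3.2). Section C.3.1.3 also labels its extra imaging analyses as exploratory.

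**The concern.** The fallback starts only when the planned test of the cognitive factors has found nothing. It then gives chance at least nine further opportunities, each presumably judged at the conventional level. A reader of the results could not tell a real single-task predictor from the best of nine null correlations. Because the same plan adjusts or labels comparable analyses, silence here cannot be read as an implied label.

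Predictors of response are half of what the study is for, and section A presents them as a basis for deciding who should be offered a scarce treatment. One chance correlation with a single test, reported after a null factor analysis, could carry weight it has not earned.

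**Working it through.** The plan states no error rate or power figure for the cognitive analyses, so there is none to reproduce.

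**Inputs from the documents.** Tasks: 3 + 2 + 2 + 2 = 9. Outcomes: 1 or 3, so 9 × 1 = 9 or 9 × 3 = 27 tests. Sample size: 50 (C.3.1.2).

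**Assumed inputs.** Two-sided Pearson tests at 0.05; task correlation 0 to 0.6; outcome correlation 0 to 0.5; one to three components retained. The documents do not settle the testing convention. The nearest power statement (C.3.1.3: n=40, r=0.38, power 0.80) comes out at 0.785 one-sided and 0.682 two-sided at 0.05.

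**Step 1: independent tests, ignoring the trigger.** The chance of at least one false hit is 1 − 0.95^m.
- m = 9: 1 − 0.95^9 = 37.0%.
- m = 27: 1 − 0.95^27 = 75.0%.
- With seven tasks instead of nine: 30.2% (m = 7) and 65.9% (m = 21).

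**Step 2: correlated tests, still ignoring the trigger.** Simulation with no true effect and n=50: task correlation 0.6 gives about 24% for one outcome; adding outcome correlation 0.5 gives about 50% for three.

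**Step 3: condition on the factors being null.** The fallback is entered only if no component is significant, on the one outcome or on any of the three. The quantity wanted is P(at least one false task hit and entry) / P(entry). Example, three components, task correlation 0.6, outcome correlation 0.5: one outcome 0.153/0.856 = 17.9%; three outcomes 0.261/0.668 = 39%. Selected results from 10,000 simulated trials per row:

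| Components | Task corr. | Outcome corr. | P(entry), 1 / 3 outcomes | False hit given entry, 1 outcome | False hit given entry, 3 outcomes |
|---|---|---|---|---|---|
| 1 | 0 | 0 | 95.1% / 85.9% | 33.8% | 71.4% |
| 1 | 0 | 0.5 | 95.2% / 87.5% | 34.7% | 67.5% |
| 1 | 0.3 | 0.5 | 94.5% / 86.7% | 29.7% | 60.5% |
| 1 | 0.6 | 0.5 | 95.3% / 87.5% | 19.5% | 43.2% |
| 3 | 0 | 0 | 86.2% / 63.6% | 30.8% | 66.5% |
| 3 | 0.3 | 0.5 | 85.9% / 67.3% | 26.4% | 54.1% |
| 3 | 0.6 | 0.5 | 85.6% / 66.8% | 17.9% | 39.0% |

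Repeat runs move the ends by about a percentage point, hence about 17–35% and about 40–71%. Conditioning lowers the rates because a task that correlates with the outcome by chance tends to carry its component with it, so null factors make single-task hits rarer.

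**Step 4: the whole two-stage procedure.** P(some factor is significant) + P(entry and a false task hit). For the last row: one outcome (1 − 0.856) + 0.153 = 29.7%; three outcomes (1 − 0.668) + 0.261 = 59.3%. Over all scenarios: about 23–41% for one outcome and 50–79% for three.

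**Step 5: with adjustment.** Bonferroni over nine independent tests: 1 − (1 − 0.05/9)^9 = 4.9%; over 27: 1 − (1 − 0.05/27)^27 = 4.9%. The critical correlation at n=50 is t/√(48 + t²): |r| = 0.28 at two-sided 0.05, and 0.39 at 0.05/9.

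**The case against.** A reader might take 37% and 75% as the false-positive rates of the fallback. They are not. They ignore the condition under which it runs, and they need independent tasks, which contradicts the shared factors that C.3.1.2 itself expects; the two Rey scores even come from the same figure. With a block structure closer to that expectation (assumed correlations 0.5–0.6 within blocks, 0.2–0.4 between, 0.8 for the two Rey scores, 0.5 between outcomes), the chance given entry is about 20–23% for one outcome and 44–49% for three with three components kept. With one component kept it is 24–28% and 51–57%.

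A reader might also infer that a null result on the cognitive hypothesis would more often than not become a positive one. For a single outcome no scenario comes near one half. For three outcomes the rate passes 50% only under some settings, such as weakly correlated tasks or fewer retained components, and the fallback sentence does not say that the secondary outcomes are included.

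Nor do the documents say that a single-task hit would confirm Hypothesis 1b or set treatment candidacy. The step is presented as additional, and because it follows a null result a careful reader would know the factor models had failed. The plan states no error rate for the step, so this is an omission and not a wrong figure.

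All of this stands, and it bounds the size of the problem. It does not remove it: the most favourable scenario is still more than three times 5%, and nothing in the text tells the analyst to adjust or to label.

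**Conclusion.** The point holds as an uncontrolled follow-up with a results-dependent trigger. Followed as written, it carries a false-predictor chance several times the nominal 5%, in the ranges given by the conditional calculation. Those ranges depend on the assumed test level and correlations, on a count of one score per listed task, and on whether one or three outcomes are tested. More scores per test, or the optional variants in the plan (percentage of possible improvement, analyses split by impairment group, adjustment for severity), could raise the number of tests. The conclusion does not depend on any single choice within the ranges. It is a cheap improvement, and it leaves the planned factor regressions as they are.

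**What to change.** Add to C.3.1.2: name the outcomes that the fallback covers; apply Holm at 5%, or a 5% false discovery rate as already used for lesion mapping, over all the task-by-outcome correlations actually run; report how many were run; and describe them as exploratory follow-up that does not count as support for Hypothesis 1b. Holm has the advantage of needing no assumption about how the tasks correlate.

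There is no need to run the correlations when the factor models succeed; that would be a preference and not part of repairing the error rate.

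The change needs one sentence and no new data. The cost is lower power for single-task findings: the rise from about 0.28 to 0.39 in the |r| required applies to the smallest p-value with nine tests, and the hurdle is higher again if all 27 are run (0.05/27 = 0.00185 for the first test). Limiting the fallback to the primary outcome would contain that loss.

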The investigators have also carried out work regarding the relationship between lesion site and treatment response, in particular investigating the role of recruitment of the non-dominant hemisphere during recovery. This work is directly relevant to the current proposal, since it provides preliminary evidence for the hypothesized role of selected brain regions in supporting recovery in response to aphasia therapy. In addition, we have available brain scan images for 6 veterans served by PIRATE, permitting a preliminary evaluation of the relationships between lesion patterns and treatment response relevant to the neuroanatomical hypotheses under Specific Aim 1.

As described briefly above, Parkinson, Raymer, Chang, FitzGerald, and Crosson^[21] studied the relationship between lesion location and extent and treatment effects in a sample of 15 patients who had received one of two semantically-oriented naming treatments. There were two major findings. First, when controlling for the extent of basal ganglia lesion, the extent of left anterior cortical lesion was positively correlated with improvement in action naming ($r = 0.821$, $p = 0.002$) and object naming ($r = 0.858$, $p < 0.0005$) on treated items (correlations with untreated items and/or standardized outcome measures were not reported). Second, when controlling for extent of left anterior cortical lesion, the extent of basal ganglia lesion was negatively correlated with treatment effects ($r = -0.785$ and -0.749 for actions and objects, respectively, both p 's ≤ 0.01). Based on these results, Parkinson, Crosson, and colleagues hypothesized that excessively “noisy” activity of the left anterior cortex may prevent adaptive re-organization from occurring in the non-dominant hemisphere (as well as in non-lesioned areas of the dominant hemisphere) to support recovery. They proposed that this interference may be reduced in the presence of more extensive lesions to the left anterior cortex and with sparing of the left basal ganglia, which has been argued to suppress peri-lesional activity during word production^[22]. These findings indicate that increased left-hemisphere involvement and intact left basal ganglia tissue should be associated with better treatment response, since both promote adaptive recruitment of other cortical resources (especially right-hemisphere tissue^[25]).

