We will use the MRICron program's nonparametric lesion mapping (NPM) feature to complete the lesion symptom correlations^[106]. These data will be structured such that there is a binary classification at the voxel level (i.e., ±lesion) and continuous behavioral data (change score associated with the different outcome measures: PNT scores and scores on acquisition/generalization probes). Since these data are likely not to satisfy parametric statistical assumptions, we will use the NPM program's Brunner-Munzel nonparametric test to relate behavioral performance on each of the treatment-outcome predictors (change scores) to lesion distributions^[107-109]. We will apply a cluster threshold of 10 contiguous voxels and threshold for a false discovery rate of .05 in order to control for type I error while maintaining sufficient power to detect effects. We will also include voxels that have at least a 25% lesion overlap across patients. VLSM analyses will focus on four principal regions of interest (ROIs): left anterior cortex, left posterior cortex, left basal ganglia, and left hippocampus. Previous work (reviewed in section B.2 above) has shown that positive response to aphasia treatment is associated with intact left hippocampus and left basal ganglia. In addition, some previous work suggests that negative treatment response is associated with more intact left anterior cortex^[21], but other work suggests that greater recruitment of left anterior cortex is associated with positive treatment response^[23]. Additional work has also found that more intact left posterior cortex is associated with more positive treatment response^[23].

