Change scores from program entry to program exit and/or follow-up will be computed for primary and secondary study measures: weekly PNT scores and acquisition/generalization probes. These scores will be correlated with lesion extent using VLSM, with analysis focusing on the four ROIs identified above. These correlations will serve to test the hypotheses relevant to Specific Aim 1 above. As predicted by Hypothesis 1c and consistent with the preliminary findings from the PIRATE participants (see B.2.1 above), we anticipate that there will be a significant negative correlation between change scores and lesion extent in left basal ganglia and hippocampus. Greater damage to structures required for learning and memory function (hippocampus) and to structures which can control maladaptive activation of damaged left-hemisphere tissue (basal ganglia) will result in poorer treatment outcomes. Also as predicted by Hypothesis 1c and consistent with preliminary data by Parkinson and colleagues (see B.2.1), we anticipate that extent of left-anterior hemisphere lesion will be positively correlated with change scores. Greater damage to left anterior cortex will prompt greater recruitment of right hemisphere cortex or other non-lesioned left hemisphere cortex, resulting in more positive treatment outcomes^[20, 25]. Furthermore, we anticipate that extent of left posterior cortex will be associated with poorer treatment outcomes, given Fridriksson's findings^[23].

Additional exploratory analyses will be carried out to examine how these neuroanatomical factors predict performance for the different outcome measures. We anticipate that brain regions which are positively correlated with change scores for acquisition probes will not be positively correlated with change scores for generalization probes, given the behavioral^[9] and neuroimaging evidence^[20] that treatment response for treated and untreated items/behaviors leans on different cognitive and neural mechanisms. We do not have any a priori predictions regarding what brain regions may be correlated with change scores for generalization probes.

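### The voxelwise test adjusts for no other region, although the evidence behind the anterior and basal ganglia predictions was mutually adjusted, so a real basal ganglia effect may be missed

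*Combined protocol and SAP*

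**What the plan says.** Section B (the preliminary work on lesion site and treatment response) describes a study of 15 patients given semantically oriented naming treatment. Both of its lesion findings are conditional:

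- Anterior cortex, with correlations of +0.821 (actions) and +0.858 (objects): "when controlling for the extent of basal ganglia lesion, the extent of left anterior cortical lesion was positively correlated with improvement in action naming".
- Basal ganglia, with correlations of -0.785 (actions) and -0.749 (objects): "when controlling for extent of left anterior cortical lesion, the extent of basal ganglia lesion was negatively correlated with treatment effects".

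Section C.3.1.3 carries both signs into Hypothesis 1c as plain correlations. It expects that "extent of left-anterior hemisphere lesion will be positively correlated with change scores" and that "there will be a significant negative correlation between change scores and lesion extent in left basal ganglia and hippocampus".

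The test is voxelwise, on a lesioned/spared indicator: "we will use the NPM program's Brunner-Munzel nonparametric test to relate behavioral performance on each of the treatment-outcome predictors (change scores) to lesion distributions". Results are thresholded at a false discovery rate of 0.05. C.3.1.3 names no covariate: not the other region, not total lesion volume, not severity. The optional severity adjustment in C.3.1.2 belongs to the cognitive regressions. If nothing is found, C.3.1.3 repeats the mapping in subgroups by aphasia severity.

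The power statement in C.3.1.3 rests on the same study. It claims power above 0.99 for correlations of 0.65 to 0.85, and 0.80 for 0.38, with 40 participants.

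**The concern.** The evidence answers a conditional question: the effect of damage in one region at a given amount of damage in the other. The planned test answers a marginal one. When two predictors have opposite effects and are positively correlated, each marginal association is pulled towards zero by the other.

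All participants have a unilateral left-hemisphere stroke, so some positive correlation between anterior and basal ganglia damage is plausible. The imaging analysis could then report no basal ganglia effect although the conditional effect behind the prediction is present. The severity subgroups would not help, because they leave the two regions unseparated in smaller samples. The stated power gives no warning, because it treats adjusted coefficients as if they were the correlations to be tested.

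**Working it through.** **The plan's own figure.** Power by Fisher's z is Φ(atanh(r)·√(N−3) − z). For r = 0.38 and N = 40, atanh(0.38)·√37 = 0.400 × 6.083 = 2.433.

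- One-sided 0.05: Φ(2.433 − 1.645) = 0.785, close to the stated 0.80.
- Two-sided 0.05: Φ(2.433 − 1.960) = 0.68.
- r = 0.65 gives 0.997 two-sided, so the claim of more than 0.99 reproduces.

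The plan states neither alpha nor sidedness for this figure. Two-sided 0.05 is used below.

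**Inputs.** The partial correlations in Section B (anterior pA, basal ganglia pB) are +0.821 and −0.785 for actions, and +0.858 and −0.749 for objects. N = 40 comes from C.1. The correlation ρ between the two lesion extents is not in the documents, so 0, 0.3, 0.5 and 0.7 are assumed.

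**From partial to unadjusted correlation.** With residual variance 1:

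- t = p/√(1−p²) and b = t/√(1−ρ²) for each region
- V = bA² + bB² + 2ρ·bA·bB + 1
- rA = (bA + ρ·bB)/√V and rB = (bB + ρ·bA)/√V

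Example, objects at ρ = 0.5: tA = 1.670 and tB = −1.130. Dividing by √0.75 gives bA = 1.929 and bB = −1.305. V = 3.720 + 1.704 − 2.518 + 1 = 3.906. So rB = (−1.305 + 0.964)/1.976 = −0.17. Then atanh(0.172)·√37 = 1.06, and power = Φ(1.06 − 1.96) + Φ(−1.06 − 1.96) = 0.19.

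Unadjusted correlation, with power in brackets (N = 40, one test):

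| ρ | Anterior, action | Basal ganglia, action | Anterior, object | Basal ganglia, object |
|---|---|---|---|---|
| 0 | +0.67 (>0.99) | −0.59 (0.98) | +0.74 (>0.99) | −0.50 (0.92) |
| 0.3 | +0.57 (0.97) | −0.45 (0.83) | +0.68 (>0.99) | −0.32 (0.53) |
| 0.5 | +0.50 (0.91) | −0.34 (0.58) | +0.65 (>0.99) | −0.17 (0.19) |
| 0.7 | +0.43 (0.80) | −0.20 (0.24) | +0.63 (>0.99) | +0.03 (0.05) |

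**Both regions in one model.** Using the stated partials with √(N−4) = 6, power exceeds 0.99 for both regions and both naming types. The partial is held at its stated value, so this figure does not vary with ρ.

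The basal ganglia correlation falls below 0.38, the plan's own detectable size, at ρ of about 0.21 (objects) or 0.43 (actions).

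**Check with the planned test.** Brunner-Munzel tests were simulated on binary lesion indicators (N = 40, 50% of participants lesioned in each region, an assumption; 1,000 runs per setting). Basal ganglia power was 0.72 (action) and 0.36 (object) at an indicator correlation of 0.3, and 0.38 and 0.07 at 0.5. A linear model with both indicators gave 1.00 in each case.

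**Weaker true effects.** With partials of ±0.65, the bottom of the range quoted in C.3.1.3, unadjusted power for either region is 0.80 at ρ = 0.3 and 0.61 at ρ = 0.5, against more than 0.99 adjusted. With ±0.45, an illustrative value only, it is 0.35 at ρ = 0.5, against 0.83 adjusted.

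**The case against.** The strongest objection is that the size of the loss depends on an unseen number. No section describes how often anterior and basal ganglia damage occur together. If the extents are uncorrelated, basal ganglia power is 0.92 to 0.98 and little is lost; cancellation needs a positive correlation. That stands. The missing adjustment is certain, and the size of the harm is not.

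The basal ganglia prediction also cites the programme's own preliminary data. Part of that section is not in the text available for review and could not be checked.

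Several stronger readings are tempting, and the documents do not support them:

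- **That all of Hypothesis 1c rests on adjusted correlations.** The hippocampal and posterior predictions come from other studies, for which no such adjustment is described.
- **That both effects would be masked.** At the source effect sizes the anterior effect survives. Both are at risk only if the true partials are weaker. C.3.1.3 expects somewhat weaker correlations but gives no value.
- **That the sign would reverse.** The only positive basal ganglia value in the table is +0.03, which is a null.
- **That the 25% lesion-overlap rule adds to the problem.** No regional lesion frequencies are given, so no effect can be shown.

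C.3.1.3 also has a reason for a rank test, namely that the data may violate parametric assumptions. A remedy should respect it.

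**Conclusion.** The concern holds for the anterior and basal ganglia predictions, with the basal ganglia effect chiefly exposed. The supporting correlations were mutually adjusted, the planned test is not, and the power statement does not notice the difference.

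For a lesion correlation between 0.3 and 0.7, basal ganglia power falls to between 0.83 and 0.24 (action) or 0.53 and 0.05 (object), where a joint model would have more than 0.99. A null basal ganglia map could therefore not be read as evidence against the hypothesis.

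This assumes a positive lesion correlation, true effects as large as in the source study, 40 scanned participants, and a single two-sided 0.05 test. Correction over many voxels would lower the unadjusted powers further. The change should be made, but the rest of the imaging plan does not depend on it.

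**What to change.** Keep the voxelwise map for localisation, and add a prespecified region-level test of these two predictions.

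1. From the normalised lesion masks that C.3.1.3 already produces, compute each participant's percentage lesioned in left anterior cortex and in left basal ganglia.
2. Regress the entry-to-exit change score on both percentages together, with rank-based or permutation inference.
3. Report both adjusted coefficients with confidence intervals, and the observed correlation between the two loads.
4. Restate power for this two-region model, giving alpha and sidedness.

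The cost is analysis-plan wording and a few hours' work on existing masks, with no new data. The downside is wider intervals if the two loads turn out to be strongly correlated.
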